## 8. STATISTICAL CONSIDERATIONS

Covariates for all analyses include sex, age, adiposity, aerobic fitness, and education unless noted otherwise.

The overarching statistical approach uses multiple regression to determine whether IR is inversely associated with outcome measures in Aims 1 and 2 and to assess mediation in Aim 3. Mean/summed outcomes (total cognition, total CBF or CP) will be predicted by HOMA-IR, for example. Not only is a composite measure calculated as a mean more reliable than the subdomain scores, but averaging multiple measures of a single construct yields a more powerful hypothesis test than using variables individually (40), under conditions we expect to hold here. This approach avoids inflation of Type I error rate as each hypothesis test examines the relationship among single variables or composites, not among multiple subdomain measures. If the test of the mean or composite score is significant, then there is no increased Type I error rate incurred in subsequent subdomain/regional tests (41).

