### 8.1. MRI Data Processing

Standard and validated tools will be used for image processing. The research team is expert in analyzing brain imaging data and have published several studies focused on MRI-derived blood flow-based measures.

Maps representing gray matter probability and cerebral blood flow will be generated using SPM, FSL, or similar software. Scans will be processed using the most up to date and recommended processing scheme, including methods previously used by our research group and collaborators.

We expect to use standard viewing software (Advanced Workstation 4.3, GE Healthcare) for magnetic resonance angiography and phase contrast data, in addition to

- 1) MIMICS and EnSight, commercial software packages commonly used in 4D flow visualization and
- 2) MatLab-based software for quantitative analysis of 4D data sets

Quantitative data from two 4D multi venc flow acquisitions will be available. The data includes:

- 1) Quantitative blood flow values (peak and mean flow, peak and mean velocity, pulsatility and resistance index) of 4D PC
- 2) Quantitative morphological data (vessel diameter) of:
  - a. Standard magnetic resonance angiography techniques
  - b. 4D PC

### 8.2. Aim 1

Composite scores will be computed by calculating and averaging z-scores within each cognitive domain. Composite total cognitive scores will be predicted from HOMA-IR and the covariates. Pilot data yielded a partial correlation of -0.6 between HOMA-IR and the total cognitive score. A one-tail test of the population correlation coefficient with a Type I error rate of 0.05 requires a sample size of **N=13** to yield power of 0.80. If this composite score test is significant, similar analyses will be performed to examine the relationship between HOMA-IR and individual cognitive ability subdomain scores.

### 8.3. Aim 2

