#### 8.3.3. Aim 2B

The change in CVC ( $\Delta\text{CVC}$ ) will be predicted from HOMA-IR and the covariates, where

$$\Delta\text{CVC} = (\text{peak CVC during OGTT}) - (\text{resting CVC})$$

Pilot data indicate the average correlation between HOMA-IR and  $\Delta\text{CVC}_{\text{MICRO}}$  of  $-0.42$ , so a one-tailed test of the partial correlation will yield power of 0.80 with a sample size of **N=31**, with Type I error rate of 0.05. We plan to assess numerous regions of interest (ROIs) linked to executive functions and memory, including frontal, temporal, and parietal regions (e.g. middle, medial, and superior frontal gyri, anterior cingulate, hippocampus, middle and superior temporal gyri, posterior cingulate, precuneus), as well as ROIs *with less involvement* in memory or executive functions (e.g. precentral and postcentral gyri, occipital cortex).  $\Delta\text{CVC}_{\text{MICRO}}$  is only predicted from HOMA-IR within an ROI, not between, to limit the number of comparisons and therefore limit the false discovery rate.

For  $\Delta\text{CVC}_{\text{MACRO}}$ , up to 11 extra- and intra cranial arteries will be studied (basilar, 2 ACA, 2 MCA, 2 PCA, 2 vertebral, and 2 ICA; dependent on individual anatomy). Total CBF will be calculated, where

$$\text{CBF}_{\text{TOTAL}} = \text{CBF}_{\text{BASILAR}} + \text{CBF}_{\text{ICA-Right}} + \text{CBF}_{\text{ICA-Left}}$$

Pilot data indicate that the average correlation between HOMA-IR and MCA perfusion during OGTT is -0.796, so that a one-tailed test of the partial correlation will yield the power of 0.80 with a sample size N=6, with Type I error rate of 0.05. For all of Aim 2, if either total CVC test is significant (micro or macro), similar regression analyses will be performed to examine the mediating effects of  $\Delta$ CVC between HOMA-IR and individual ROI (micro) or artery (macro)  $\Delta$ CVC values.

#### 8.4. Aim 3

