Aim 3 tests the mediation effects of CVC on the relationship between HOMA-IR and the composite cognition scores assessed in Aim 1. Mediation will be assessed using the test of joint significance (23). The path between HOMA-IR and perfusion will have been examined in Aim 2. At rest (Aim 3A), mean  $CVC_{MICRO}$  and  $CVC_{MACRO}$  will be examined as the primary mediating variables. Pilot data indicate the correlation between resting  $CVC_{MICRO}$  and cognition is 0.37, so that a sample size of **N=41** would yield 0.8 power in a one-tailed test and Type I error rate of 0.05. During OGTT (Aim 3B), mean peak  $\Delta$ CVC will be the primary mediator variable. Pilot data indicate that the partial correlation between post-OGTT  $\Delta CVC_{MICRO}$  and the total cognitive score was 0.4, so that a directional test of this path requires a sample size of **N=34** to yield the power of 0.8 with Type I error rate of 0.05. A similar power is achieved for  $CVC_{MACRO}$ . If either test (rest or OGTT challenge) is significant, analyses will be performed to examine the mediating effects of CVC between HOMA-IR and individual cognitive ability domain scores.

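### The sentence that sets the Aim 2 regional follow-up specifies mediation by ΔCVC, contradicts the rest of the plan, and if followed would not test whether HOMA-IR affects a region

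*Combined protocol and SAP*

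**What the plan says.** The last sentence of 8.3.3 applies to the whole of Aim 2. Its condition is "if either total CVC test is significant (micro or macro"), and its instruction is "similar regression analyses will be performed to examine the mediating effects of" ΔCVC between HOMA-IR and the ΔCVC of each ROI (micro) or artery (macro). The mediator is not described as the total.

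Other parts of the plan bear on the same analysis:

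- Section 8 gives the overall approach: multiple regression for the inverse association of IR with outcomes in Aims 1 and 2, and for mediation in Aim 3. It adds that "Mean/summed outcomes (total cognition, total CBF or CP) will be predicted by HOMA-IR", and that regional tests following a significant composite carry no extra Type I error.
- Earlier in 8.3.3, microvascular ΔCVC "is only predicted from HOMA-IR within an ROI, not between, to limit the number of comparisons".
- In 8.3.3, "up to 11 extra- and intra cranial arteries will be studied". Total CBF is defined there as the basilar plus the two ICAs.
- In 8.2 (Aim 1), the parallel follow-up is a direct association: "similar analyses will be performed to examine the relationship between HOMA-IR and individual cognitive ability subdomain scores".
- In 8.4 (Aim 3), "Mediation will be assessed using the test of joint significance (23"), with mean CVC or mean peak ΔCVC as the mediator of cognition.

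**The concern.** Mediator and outcome in the closing sentence are the same kind of quantity. The follow-up opens only after a total test is significant, so the natural candidate for the mediator is the total or mean ΔCVC. When the total test that opened it is the ΔCVC test, the path from HOMA-IR to the mediator has already been declared significant. All that remains is whether the region moves with the total at a given HOMA-IR, and that says nothing about whether HOMA-IR affects the region.

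The regional results carry the hypothesis of regional specificity in the project summary. Section 8.3.3 includes regions with less involvement in memory or executive function ("e.g. precentral and postcentral gyri, occipital cortex") alongside the memory and executive regions. A test that flags both sets equally often cannot support that comparison, and section 8's Type I error statement would not hold for it.

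There is also a gap. The sentence covers all of Aim 2, but both its mediator and its outcome are changes during the OGTT. A significant resting result in Aim 2A therefore leads to no resting regional analysis.

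**Working it through.** **1. The plan's own figures.** For a one-tailed test of a correlation, λ = r√N/√(1−r²) with N−2 degrees of freedom. With r = 0.42 (absolute value):

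- N=31: λ = 0.42 × 5.568/0.9075 = 2.577, critical t = 1.699, power 0.808. N=30 gives 0.796, so the stated N=31 reproduces.
- N=55: λ = 3.432, critical t = 1.674, power 0.959, against the stated 0.95.

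The other stated sample sizes (13, 55, 6, 41, 34) also reproduce exactly. None of these figures concerns the regional follow-up, for which the plan states no operating characteristic.

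**2. Inputs for the follow-up.**

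- From the documents: N=55; one-tailed 0.05; r = −0.42 between HOMA-IR and ΔCVC (micro); five covariates plus intracranial volume, making six; 12 regions named as examples, three of them in the less-involved list.
- Assumed: the mediator is the mean of the regions; Aim 3's joint-significance test carries over; the −0.42 applies to the total; three of the 12 regions have no HOMA-IR effect; variances are equal; covariates are independent of HOMA-IR; residual inter-region correlation ρ is 0 to 0.5.

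**3. What the second path measures.** If the mediator is the mean of K regions, the squared partial correlation of a region with it, given HOMA-IR, is

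r² = [1 + (K−1)ρ]/K.

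The HOMA-IR effect on the region does not appear in this expression. The regression has nine parameters (intercept, total, HOMA-IR, six covariates), so df = 55−9 = 46 and critical t = 1.679. The noncentrality is about r/√(1−r²) × √47, where 47 = 55−8.

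- K=12, ρ=0: r² = 1/12 = 0.083, λ = 2.07, power 65%.
- K=12, ρ=0.1: r² = 2.1/12 = 0.175, λ = 3.16, power 93%.
- K=12, ρ=0.3: r² = 4.3/12 = 0.358, λ = 5.12, power above 99%.
- K=30, ρ=0: r² = 1/30 = 0.033, λ = 1.27, power 35%.

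**4. Simulation.** Share of regions flagged among trials that passed the total test (about 92% to 93% of trials), K=12:

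| ρ | Mediation, unaffected region | Mediation, affected region | Direct, unaffected region | Direct, affected region |
|---|---|---|---|---|
| 0 | 64.5% | 64.2% | 5.1% | 35.3% |
| 0.1 | 91.8% | 91.1% | 5.1% | 57.4% |
| 0.3 | 99.9% | 99.8% | 5.4% | 82.9% |
| 0.5 | 100% | 100% | 5.4% | 94.9% |

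With 30 regions, eight of them unaffected, mediation flags an unaffected region in 34% (ρ=0) or 99.7% (ρ=0.3). The simulation agrees with step 3. Mediation flags affected and unaffected regions equally often; direct regression separates them.

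**5. Overlap or shared variance.** Leaving the region out of the mean lowers the rate for an unaffected region to 4.8% at ρ=0, but it is still 97.8% at ρ=0.3. Part-whole overlap explains the result only when regions are uncorrelated. Otherwise shared variance is enough.

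**6. Arteries.** The list has 1 basilar + 2 ACA + 2 MCA + 2 PCA + 2 vertebral + 2 ICA = 11. Three of these (basilar, two ICAs) are terms of total CBF; 11−3 = 8 are not. For an unaffected component of a three-artery total, with the same r = −0.42 assumed, mediation flags it in 99.7% to 100% and direct regression in 5.6% to 6.4%. For the other eight the rate depends on their correlation with the total, which the documents do not give.

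**The case against.** The best defence is that this is a drafting slip. Section 8 places mediation in Aim 3, 8.3.3 itself describes direct prediction from HOMA-IR within a region, and the closing sentence closely resembles the one that ends Aim 3, where mediation belongs. An analyst guided by section 8 would run the right test. This largely stands, and it rules out one inference a reader might draw: that the plan as a whole cannot separate affected from unaffected regions. The plan also describes an analysis that can. The documents do not say which instruction prevails, however, and the within-region statement covers only the microvascular arm. For arteries, the closing sentence is the only specific follow-up instruction.

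A reader might also infer that every outcome is contained in its own mediator. The documents do not support that. The sentence does not name the total as mediator, and eight of the 11 arteries, including both MCAs, are not terms of total CBF. Containment holds for the basilar and ICAs, and for ROIs if total CP is their mean.

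Finally, the simulated rates depend on inputs the plan does not fix: the ROI lists are only examples, inter-region correlation is not given, and joint significance is specified only for Aim 3. That is why a range is shown. The analysis is also a gated secondary one.

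**Conclusion.** The point holds as an internal contradiction with a material consequence if the wrong sentence is followed. The closing sentence of 8.3.3 conflicts with section 8 and with the within-region statement in the same section, and it gives Aim 2A no resting regional follow-up. Taken literally, with the total or mean ΔCVC as mediator and Aim 3's joint-significance test, it flags a region that HOMA-IR does not affect in roughly 64% to 100% of trials reaching the follow-up, under the assumptions listed for 12 regions and ρ from 0 to 0.5. The rate is 34% with 30 uncorrelated regions. Direct regression flags it in about 5%. The direction is firm because the second path does not contain the regional HOMA-IR effect; the exact percentages are conditional.

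The point does not extend to the total-CVC tests, the sample size of 55 or the stated power figures, which reproduce.

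**What to change.** Replace the closing sentence of 8.3.3 with wording such as:

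> If the total CVC (Aim 2A) or total ΔCVC (Aim 2B) test is significant, the corresponding ROI (micro) or artery (macro) CVC or ΔCVC values will each be regressed on HOMA-IR and the covariates.

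Keep mediation for Aim 3 only. This brings 8.3.3 into line with section 8, the within-region statement and the Aim 1 follow-up, and gives the resting analysis its missing regional step. The cost is one sentence, with no new data, procedures or participants.

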#### 8.5. Statistical Summary

With **N=55** for the overall grant, power in Aim 1 increases to near unity, power in Aim 2A is 0.8, power in Aim 2B increases to 0.95, power in Aim 3A increases to 0.9, and that in Aim 3B increases to 0.94, providing this study with sufficient to outstanding power to test the hypotheses of interest.

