#### 8.3.2. Aim 2A

Total CVC will be predicted from HOMA-IR and the covariates (intracranial volume is an additional covariate for CVC analyses). Resting CP data indicate reduced perfusion in several anterior brain regions. Pilot data yielded a correlation between HOMA-IR and resting  $\text{CVC}_{\text{MICRO}}$  of  $-0.324$ , such that a sample of size **N=55** will yield the power of 0.8 in a one-tailed test of the correlation, with Type I error rate of 0.05. In contrast, we will test, but do not expect, resting  $\text{CVC}_{\text{MACRO}}$  to be related to HOMA-IR, since resting  $\text{CVC}_{\text{MACRO}}$  is similar in low and high IR.

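### The Aim 3 powers of 0.9 and 0.94 cover only the CVC–cognition path; the joint test for resting CVC_MICRO cannot exceed the plan's own 0.8 for Aim 2A

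*Combined protocol and SAP*

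**What the plan says.** Section 8.4 sets the decision rule for Aim 3: "Mediation will be assessed using the test of joint significance (23"). It assigns the first leg elsewhere: "The path between HOMA-IR and perfusion will have been examined in Aim 2". The only effect sizes it gives for Aim 3 concern the second leg.

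- **Aim 3A (rest).** The pilot correlation between resting CVC_MICRO "and cognition is 0.37, so that a sample size of" 41 gives power 0.8, one-tailed at 0.05. Mean CVC_MICRO and mean CVC_MACRO are both named as primary mediators.
- **Aim 3B (OGTT).** The pilot partial correlation between the change in CVC_MICRO and total cognition is 0.4, "so that a directional test of this path requires a sample size of" 34. The section then adds, for CVC_MACRO, "A similar power is achieved for" that measure. It gives no correlation and does not say whether the resting value or the change is meant.

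Section 8.5 carries these forward to N=55: "power in Aim 3A increases to 0.9, and that in Aim 3B increases to 0.94, providing this study with sufficient to outstanding power". The same sentence also states "power in Aim 2A is 0.8". That last figure comes from section 8.3.2, where r=−0.324 between HOMA-IR and resting CVC_MICRO at N=55 "will yield the power of 0.8 in a one-tailed test of the correlation, with Type I error rate of 0.05". Section 8.3.2 also says that no relation between HOMA-IR and resting CVC_MACRO is expected.

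**The concern.** A joint-significance test declares mediation only when both legs are significant. Its power is the probability that both tests succeed, and this cannot exceed the probability that the weaker one does. The plan gives 0.8 for one leg of the resting CVC_MICRO pathway and 0.9 for the whole pathway, and the two cannot both be right.

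Section 8.5 is the plan's only statement of how likely 55 subjects are to detect mediation, and it ends by calling the power sufficient to outstanding. If Aim 3A is null, a reader who trusts 0.9 will treat the result as fairly strong evidence against resting mediation. The design does not support that reading.

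**Working it through.** **Inputs.** N=55, one-tailed 0.05 (sections 8.2 to 8.5). HOMA-IR to CVC_MICRO: −0.324 at rest (8.3.2) and −0.42 for the change (8.3.3). CVC_MICRO to cognition: 0.37 at rest and 0.4 for the change (8.4). HOMA-IR to cognition: −0.6, labelled partial (8.2).

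**Step 1: reproduce the plan's figures.** Use the one-sided t test of a single correlation, with noncentrality δ = r√N / √(1−r²) and N−2 degrees of freedom. This returns every stated sample size for 0.80 power: 13, 55, 31, 6, 41 and 34. At N=55 (53 df, critical t = 1.674):

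| Path | abs(r) | δ | Power | Section 8.5 |
|---|---|---|---|---|
| 2A: HOMA-IR to resting CVC_MICRO | 0.324 | 2.540 | 0.806 | 0.8 |
| 3A: resting CVC_MICRO to cognition | 0.37 | 2.954 | 0.898 | 0.9 |
| 2B: HOMA-IR to change in CVC_MICRO | 0.42 | 3.432 | 0.959 | 0.95 |
| 3B: change in CVC_MICRO to cognition | 0.40 | 3.237 | 0.939 | 0.94 |

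The Aim 3 figures are therefore single-path powers.

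**Step 2: upper bound.** P(both) ≤ min(P₁, P₂). For resting CVC_MICRO this is min(0.806, 0.898) = 0.806, whatever the dependence between the two tests. For the change it is min(0.959, 0.939) = 0.939, so 0.94 is the best case.

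**Step 3: product of the plan's own powers**, treating the two tests as independent.

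- Aim 3A: 0.806 × 0.898 = 0.724.
- Aim 3B: 0.959 × 0.939 = 0.901.

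For scale, the smallest N at which the product reaches 0.8 is 65 for Aim 3A and 44 for Aim 3B.

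**Step 4: simulation.** 40,000 trivariate-normal samples at N=55, testing r(HOMA-IR, CVC) < 0 and partial r(CVC, cognition given HOMA-IR) > 0. With the pilot 0.37 and 0.4 taken as already conditional on HOMA-IR:

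| | No covariates | Six covariates |
|---|---|---|
| Aim 3A | 0.69 | 0.62 |
| Aim 3B | 0.87 | 0.82 |

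The six covariates are sex, age, adiposity, fitness, education and intracranial volume.

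**Step 5: if the pilot values are not conditional on HOMA-IR.** The second path then needs (r_MY − r_XM·r_XY) / √[(1−r_XM²)(1−r_XY²)], where X is HOMA-IR, M is CVC and Y is cognition. The range for r_XY is assumed, from −0.6 to −0.2.

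| r_XY | 3A partial r | 3A joint (0 / 6 covariates) | 3B partial r | 3B joint (0 / 6 covariates) |
|---|---|---|---|---|
| −0.6 | 0.232 | 0.41 / 0.36 | 0.204 | 0.42 / 0.37 |
| −0.4 | 0.277 | 0.52 / 0.45 | 0.279 | 0.63 / 0.57 |
| −0.2 | 0.329 | 0.62 / 0.56 | 0.355 | 0.80 / 0.75 |

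**Step 6: resting CVC_MACRO.** If its relation to HOMA-IR is null, as section 8.3.2 expects, and its partial correlation with cognition is 0.37, the joint test passes about 4% of the time. That is a false-positive rate, not power.

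**The case against.** The best defence is that nothing was miscalculated. Every stated N and power reproduces, section 8.4 says the first leg belongs to Aim 2 and describes the Aim 3B calculation as a test of one path, and section 8.5 prints the Aim 2A power beside the Aim 3A power. A careful reader could work out which path each figure covers, or read the Aim 3 powers as conditional on Aim 2 having succeeded. It is fair to call the fault one of labelling. But section 8.5 lists all five powers in parallel as power for the hypotheses, with no such condition, and the Aim 3 hypothesis in section 3.3 is mediation, which one path cannot establish.

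Three narrower points have some force.

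- Aim 3A has two primary mediators. If success through either one counts, the strict bound is 0.80 + 0.05 = 0.85, the extra 0.05 being a false positive through a null CVC_MACRO path. That is still below 0.9.
- For Aim 3B, the natural reading of the partial 0.4 is that it is conditional on HOMA-IR, which leaves only a modest overstatement. For the macrovascular change, section 8.3.3 gives −0.796 for the MCA. If that carries over to the total, the first path has power near 1 and the joint figure is set by the second path. The remark about similar power for CVC_MACRO probably concerns this change, since it follows the Aim 3B sentence, but the plan does not say so.
- The zero-order ranges in Step 5 rest on an assumed HOMA-IR–cognition correlation, and by section 3 the pilot values come from 7 subjects for Aim 1 and 5 for Aims 2 and 3. They are indicative only, and the conclusion does not depend on them.

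N=55 was set by Aim 2A, so no design decision depends on the Aim 3 figures.

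**Conclusion.** The concern holds. For resting CVC_MICRO, a power of 0.9 is incompatible with the plan's own test and its own 0.8 for Aim 2A. This follows from the probability bound alone, without any assumption about independence or pilot adjustment. The risk of missing a real resting mediation is at least about 20% rather than 10%. It is about 28–38% (power 0.72 to 0.62) if 0.37 is conditional on HOMA-IR, and higher if it is not.

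For Aim 3B, 0.94 is the best case. With 0.4 conditional on HOMA-IR, and the average pilot correlation of −0.42 taken to apply to the composite, joint power is 0.82 to 0.90. No mediation power can be claimed for resting CVC_MACRO while the plan expects its first path to be null.

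**What to change.** In sections 8.4 and 8.5:

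1. Restate the Aim 3A and 3B powers for the joint-significance test, with the second path conditional on HOMA-IR and the covariates. If the single-path figures are kept, label them as such and give the joint figures beside them.
2. State what each pilot correlation (0.37, 0.4 and −0.6) was adjusted for.
3. Remove the description of power as sufficient to outstanding for Aim 3A, and for Aim 3B unless 0.4 is confirmed as conditional on HOMA-IR.
4. State that no power is claimed for mediation through resting CVC_MACRO. Say which CVC_MACRO measure the similar-power remark refers to, and on what correlation it rests.

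The cost is rewording only. The stated power for Aim 3A becomes less favourable. No additional subjects are needed, and procedures and analyses stay as they are.

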## 9. DATA AND RECORD KEEPING

### 9.1. Data Management

Delegated and appropriately trained study team members will be involved in data collection. All personnel who will be involved in data collection have completed appropriate Human Subjects Protection training or will before they engage in contact with subjects and subject data.

The Research Electronic Data Capture (REDCap) system is used to manage the data for this study. REDCap is a largely self-service, secure, web-based application for building and managing data collection forms. REDCap provides data management functionality by allowing the development of instruments and surveys to support data capture for research studies.

The REDCAP system used for this study is managed by ICTR. The ICTR REDCap support team will work with the investigator, statistician, and study team to ensure the relevant, applicable study data are collected and managed with restricted access using the software electronic data collection form instruments.

